We attempted to collect outcome measures at the following timepoints: 1) within one month before starting treatment; 2) within the last day of pre-FR stage through the first day of FR stage; 3) on the last day of FR; 4) 3- and 5) 6- months after the end of FR. However, this precise collection schedule was not always possible. For example, baseline measures were collected more than one month before the start of treatment for study subjects who had conflicts such as military training exercises, personal or family illness or planned leisure travel which postponed the start of study treatment. Collection of follow-up measures was sometimes earlier or later than desired when study subjects with conflicts were unavailable at the time outcomes were requested. We plan to compare outcomes collected within the above timeframes with those collected within timeframes with modest and moderate flexibility as outlined in section 11.3. This analysis will inform the design of future pragmatic clinical trials in determining acceptable timeline parameters for collection of pain outcomes.

Aim 7: Determine if patient activation, pain catastrophizing, self-efficacy or pain acceptance moderates or mediates pain and function outcomes.

We will determine if level of patient activation, catastrophizing, self-efficacy and pain acceptance as measured by legacy questionnaires completed by study subjects have an impact on pain and functional outcomes.

9.5 Study Design:

Describe study design in one to two sentences (e.g., prospective, use of existing records/data /specimens, observational, cross-sectional, interventional, randomized, placebo-controlled, cohort, etc.). Specify the phase – Phase I, II, III, or IV – for FDA-regulated investigational drug research

A comparative effectiveness study, using a prospective randomized cohort design, with patients assigned to either (i) a course of integrative pain management modalities (IM) or (ii) standard care (SC), for three weeks prior to beginning a course of FR.

9.6 Target Population:

Describe the population to whom the study findings will be generalized

Active duty service members with chronic pain

9.7 Benefit to the DoD:

State how this study will impact or be of benefit to the Department of Defense

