During the course of the study, a protocol modification was approved to allow subjects to participate in the FR program with an extended 2 days per week over 6 week schedule with the same number of treatment hours as the original 4 days per week for 3 weeks. We will evaluate outcomes in both groups to determine if one treatment approach yielded superior outcomes to the other.

Analytical Technique: We will use a Sequential Multiple Regression model.⁷⁹ We will assess the relative importance of the FR delivery method (either 4 days per week x 3 weeks vs. 2 days per week x 6 weeks controlling for treatment group on our primary outcomes of pain and physical function as well as on the secondary outcomes measures (depression, anxiety, anger, sleep quality, fatigue, medical board status for disability, duration of pain-related disability, prescription opioid dosage, and functional capacity tests for endurance and strength).

Aim 6: Compare outcome measures collected within narrow timelines to those collected within flexible timelines.

We attempted to collect outcome measures at the following timepoints: 1) within one month before starting treatment; 2) within the last day of pre-FR stage through the first day of FR stage; 3) on the last day of FR; 4) 3- and 5) 6- months after the end of FR. However, this precise collection schedule was not always possible. For example, baseline measures were collected more than one month before the start of treatment for study subjects who had conflicts such as military training exercises, personal or family illness or planned leisure travel which postponed the start of study treatment. Collection of follow-up measures was sometimes earlier or later than desired when study subjects with conflicts were unavailable at the time outcomes were requested. We plan to compare outcomes collected within the above timeframes with those collected within timeframes with modest and moderate flexibility as outlined in the following table. This analysis will inform the design of future pragmatic clinical trials in determining acceptable timeline parameters for collection of pain outcomes.

	Baseline	End of pre-FR stage	End of FR stage	Short-term	Intermediate-term
Narrow timelines	w/in 1 month of treatment start	Last day of pre-FR up to start of FR	Last day of FR	3 months after end of FR	6 months after end of FR

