Modest flexibility	w/in 2 months of treatment start	\leq 2 treatment days before end of pre-FR, through \leq 2 treatment days after start of FR	\leq 2 treatment days before end of FR, through \leq 7 calendar days after end of FR	2-4 months after end of FR	5-7 months after end of FR
Moderate flexibility	w/in 3 months of treatment start thru 2 days after treatment start	\leq 2 treatment days before end of pre-FR, through \leq 4 treatment days after start of FR	\leq 2 treatment days before end of FR, through \leq 30 calendar days after end of FR	1-<5 months after end of FR	6-9 months after end of FR

Analytical Technique: We will use a Sequential Multiple Regression model.⁷⁹ We will assess the relative importance of the timing of assessments on our primary outcomes of pain and physical function as well as on the secondary outcomes measures (pain interference, depression, anxiety, anger, sleep quality, fatigue, medical board status for disability, duration of pain-related disability, prescription opioid dosage, and functional capacity tests for endurance and strength). We will code an indicator variable to document every observation that occurs within the narrow timeline. We will use an interaction term of this indicator with the intervention to see if the intervention shows a differential effect for those who adhere to the narrow assessment timelines.

Aim 7: Determine if patient activation, pain catastrophizing, self-efficacy or pain acceptance moderate or mediates pain and function outcomes.

We will determine if level of patient activation, catastrophizing, self-efficacy and pain acceptance as measured by legacy questionnaires completed by study subjects have an impact on pain and functional outcomes.

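### Aim 6 codes assessment timing only as narrow or not narrow, so it does not give the promised comparisons with modest and moderate flexibility; the moderate 6-month window also fails to contain the modest one

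*Combined protocol and SAP*

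**What the plan says.** Section 11.3, under Aim 6, states: "We plan to compare outcomes collected within the above timeframes with those collected within timeframes with modest and moderate flexibility". Section 9.4 makes the same promise, referring to "timeframes with modest and moderate flexibility as outlined in section 11.3". The stated purpose is to help future pragmatic trials decide which timing limits for pain outcomes are acceptable.

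A table in section 11.3 then sets out three rows (narrow, modest, moderate) for five assessment points. The two follow-up columns read as follows.

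- Short-term: modest "2-4 months after end of FR", moderate "1-<5 months after end of FR".
- Intermediate-term: modest "5-7 months after end of FR", moderate "6-9 months after end of FR".

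The narrow row gives 3 and 6 months after the end of FR for these two columns, with no tolerance on either side.

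The analytical technique is a sequential multiple regression that assesses the importance of assessment timing. The only coding given for timing is: "We will code an indicator variable to document every observation that occurs within the narrow timeline". It continues: "We will use an interaction term of this indicator with the intervention".

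**The concern.** There are two separate mismatches.

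The first is between the promise and the model. Three tiers are defined and two comparisons with narrow are announced, but the one timing variable has two levels. Modest visits, moderate visits and any visits outside every window fall into the same reference group. The analysis could then show whether leaving the narrow window matters. It could not show whether the answer depends on how far the window is relaxed, which is what a designer choosing a window needs to know.

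The second is inside the table. Moderate flexibility should accept whatever modest flexibility accepts, and it does so in four columns. In the intermediate-term column the lower limit moves later, from 5 to 6 months. If the rows are applied as tiers or as cumulative inclusion windows, relaxing the rule removes some visits while adding others. A change in results between the tiers could then not be put down to looser timing alone.

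**Working it through.** The plan states no figure to reproduce. The check compares the windows with one another and counts model terms.

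**Step 1: does the modest window lie inside the moderate one?** Inputs are the cells of the Aim 6 table. Baseline is read as time before treatment start, as the Aim 6 text does for the narrow window. The condition is that the moderate lower limit is no later than the modest lower limit, and the moderate upper limit is no earlier than the modest upper limit.

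| Assessment | Modest | Moderate | Contained? |
|---|---|---|---|
| Baseline | up to 2 months early | up to 3 months early, 2 days late | yes |
| End of pre-FR | 2 treatment days early, 2 late | 2 early, 4 late | yes |
| End of FR | 2 treatment days early, 7 calendar days late | 2 early, 30 late | yes |
| Short-term | 2 to 4 months | 1 to <5 months | yes |
| Intermediate-term | 5 to 7 months | 6 to 9 months | no |

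In the last column the overlap is 7 − 6 = 1 month, out of a modest width of 7 − 5 = 2 months. Half the width of the modest window therefore lies outside the moderate one. Measured from the 6-month target, the early allowance falls from 1 month to 0. A visit at 5 to <6 months meets the modest row, fails the moderate row, and is also too late for the moderate short-term window, which ends before 5. A gap between adjacent windows is not itself the fault, since the modest row also leaves >4 to <5 months uncovered. The fault is the failure to nest.

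**Step 2: how many terms does the promise need?** Three tiers (narrow, modest only, moderate only) need 3 − 1 = 2 contrasts and 2 interactions with arm. The plan defines 1 contrast and 1 interaction.

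**Step 3: can the direction of the window effect be known?** No; the documents give no distribution of visit times. As an illustration only, take 6-month visits as normally distributed with SD 0.5, 1 or 1.5 months.

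- Centred on 6 months: the 5–7 window accepts 95%, 68% or 50% of visits, and the 6–9 window 50%, 50% or 48%.
- Centred on 7 months: the 5–7 window accepts 50%, 48% or 41%, and the 6–9 window 98%, 82% or 66%.

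The order of the two tiers reverses with the assumed centre, so these figures show only that it could go either way.

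**Step 4: what precision would tiered coding have?** Assume 152 patients (the required sample in section 11.2), one visit each, 1:1 arms, and half of visits narrow (n = 76). In SD units, an arm difference within a tier of n patients has variance 4/n, so a tier-by-arm contrast has SE = √(4/n₁ + 4/n₂). The difference detectable with 80% power at two-sided 5% is 2.80 × SE.

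- Narrow versus all others (76 and 76): SE 0.32, detectable 0.91 SD.
- Narrow versus a tier holding 30% of visits (76 and 45.6): SE 0.37, detectable 1.05 SD.
- Narrow versus a tier holding 15% of visits (76 and 22.8): SE 0.48, detectable 1.34 SD.

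The tier shares are assumptions. The plan codes every observation and schedules up to five assessments per patient, so one visit per patient is a simplification.

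**The case against.** The strongest reply is that the two halves pull against each other. Under the single indicator as written, a visit at 5 to <6 months is simply not narrow, and the 6–9 cell plays no part. The cell matters only if the rows serve as inclusion windows. In that case, fitting the narrow indicator first within the modest window and then within the moderate one would give both promised comparisons. This is a fair account of how the analysis could be rescued, but the plan does not say that it will be done. As printed, moving from the first fit to the second would also lose the visits at 5 to <6 months.

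It can also be said that Aim 6 is headed as narrow versus flexible, which the indicator answers, and that pooling the flexible tiers is a defensible way to keep precision. Both points are right as far as they go. They do not deliver the comparisons that two sections announce and a three-row table sets up.

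A reader might go further and infer that the plan promises a direct modest-versus-moderate contrast. It does not; each flexible tier is to be set against narrow. Nor do early 6-month visits have a contradictory status: under a tier factor they are modest only, even with the printed limits. No sentence requires the rows to nest. That expectation comes from the labels and the other four columns, so the cell looks like a slip, but the documents do not show which limit was intended.

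**Conclusion.** The point holds and is minor. The defined coding answers narrow versus everything else and does not provide separate narrow-versus-modest and narrow-versus-moderate comparisons. One of five columns fails to nest, which has consequences only if the rows are used as tiers or cumulative windows. These conclusions rest on the printed text and on no assumption about visit times.

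A related gap bears more directly on the analysis as written. The narrow 3- and 6-month cells carry no tolerance, so the one planned indicator cannot be coded unambiguously at two of the five assessment points.

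A reader might infer that the looser 6-month tier will accept fewer visits than the stricter one, or that the trial's main result is at risk. The documents support neither. The number of visits affected is unknown and the direction depends on when visits took place. The primary comparison, at 3 months under Aim 1, does not use the Aim 6 indicator, and the short-term windows nest.

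**What to change.** 1. Reconcile the intermediate-term cell so that the moderate window contains the modest one. The sponsor should state the intended limits.
2. Code timing as a factor with levels narrow, modest only and moderate only, with its interaction with arm. Alternatively, fit the narrow indicator within the modest window and then within the moderate window. The plan should say which, because in the second fit the comparison group also includes the modest-only visits.
3. State whether visits outside every window are excluded or kept as a separate level.
4. Give the narrow 3- and 6-month cells an explicit tolerance.
5. Report tier results as estimates with intervals, not as tests of which window is acceptable.

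The cost is a few table cells and some analysis-plan wording, with no new data. With the factor, each outcome model gains one contrast and one interaction. The downside is low precision per tier: under the assumptions above, only tier-by-arm differences of about 1.05 to 1.34 SD against narrow would be detectable, compared with 0.91 SD for the pooled indicator. The gain is therefore mainly descriptive.

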Primary (i.e., primary outcome variables) and secondary endpoints. The primary outcome endpoints are pain intensity and functional status as measured by the PASTOR questionnaire. In addition, secondary predictors of outcomes measures will be evaluated, including demographic factors (age, military rank, household income, race), measures of pain interference, depression, anxiety, anger, sleep quality, fatigue, medical board status for disability, duration of pain-related disability, prescription opioid dosage and functional capacity tests for endurance and strength.

Data analysis.

Aim 1: Evaluate the benefit of a program of multimodal integrative pain management therapies prior to an intensive functional restoration program, relative to standard care.

Hypothesis: Patients who complete an IM program prior to an FR program will demonstrate significantly greater improvements in pain and physical function going into the FR program, relative to standard care. At post-FR, patients who completed an IM program prior to FR will demonstrate significantly improved outcomes on pain severity and physical function at discharge from the program and at 3-months post-FR, relative to standard care.

Analytical Technique: We will use a hierarchical linear model (HLM) for a cluster-randomized trial with time nested within patients.⁷⁷ HLM affords an integrated approach to studying the structure and predictors of individual change, and provides the appropriate standard errors and correct statistical inferences for clustered data. HLM models allow the use of data from patients who are missing one or more observations, where the assumption holds that data are missing at random. Some patients will not follow the intervention protocol, either deliberately by not doing the intervention or due to extenuating circumstances that prevent their participation with the intervention protocol. We will use an intent-to-treat analysis.

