Analytical Technique: The co-primary outcomes for pain severity and physical function will be analyzed using a Sequential Multiple Regression model.⁷⁹ The model will adjust for baseline measures of the co-primary outcomes and pre-FR treatment groups, before assessing the relative importance of secondary outcomes measures (baseline measures of pain interference, depression, anxiety, anger, sleep quality, fatigue, medical board status for disability, duration of pain-related disability, prescription opioid dosage, and functional capacity tests for endurance and strength). Relative importance of predictors among these secondary outcomes will be reported by their respective regression beta weight coefficients. To control for inflation of Type I error rates due to co-primary outcomes, alpha will be set to 0.025 for each test of the outcome variables in their respective regression models.

Aim 3: Evaluate the relationship between legacy paper questionnaires included in the PASTOR-plus packet with PASTOR submeasures.

We will compare legacy paper questionnaires completed by study subjects which include the Tampa Kinesiophobia Questionnaire, Patient Activation Measure, Pain Self-Efficacy Questionnaire, Chronic Pain Acceptance Questionnaire and Roland-Morris Disability Questionnaire, and Pain Catastrophizing Scale with PROMIS measures included in the electronic PASTOR assessment, including pain interference, depression, anxiety, anger, and physical function. This will determine if there are legacy questionnaires with prognostic value which should be added to PASTOR.

Analytical Technique: We will use correlation analysis to determine the relationship between legacy paper questionnaires and PASTOR submeasures.

Aim 4: Evaluate the relationship between self-reported physical function (from PASTOR) and clinician-supervised tests of physical function, such as exercise treadmill test at all timepoints.

We will compare self-reported physical function with clinician-supervised tests of physical function to determine if PASTOR respondents over or under-estimate their physical capacity.

Analytical Technique: We will use correlation analysis to explore the relationship between self-report and clinician supervised tests of physical function.

Aim 5: Determine whether outcomes differ between the subgroup of participants who completed FR program 4 days per week x 3 weeks vs 2 days per week x 6 weeks.

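### Aim 6 codes assessment timing per observation, with up to five observations per patient, but names a multiple regression with no allowance for within-patient correlation; if visits are pooled, its timing and timing-by-intervention tests can be too liberal

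*Combined protocol and SAP*

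**What the plan says.** Section 11.3, Aim 6, schedules five assessments: baseline, the end of the pre-FR stage, and then "3) on the last day of FR; 4) 3- and 5) 6- months after the end of FR". Under Analytical Technique the model is given as "We will use a Sequential Multiple Regression model". Timing is then coded: "We will code an indicator variable to document every observation that occurs within the narrow timeline". The key test follows: "We will use an interaction term of this indicator with the intervention to see if the intervention shows a differential effect". The outcomes are pain and physical function, plus a list of secondary measures that includes medical board status. No random effect, clustered standard error, visit term or alpha is given for this aim.

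On why assessments went off schedule, the same section says: "Collection of follow-up measures was sometimes earlier or later than desired when study subjects with conflicts were unavailable". The reasons listed include training exercises, illness and travel.

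Aim 1, in the same section, handles the repeated scores differently: "We will use a hierarchical linear model (HLM) for a cluster-randomized trial with time nested within patients". The reason given is that HLM "provides the appropriate standard errors and correct statistical inferences for clustered data". Section 11.1 also mentions mixed models, but only when discussing missing data, and it refers the reader to section 11.3 for the method of each aim.

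**The concern.** Repeated scores from one patient are correlated. A multiple regression that stacks them as separate rows counts them as independent information. For a predictor that also tends to repeat within a patient, such as being late, the standard error then comes out too small and the test rejects too often. The timing-by-arm interaction has the same problem, because arm is constant within a patient.

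There is a second issue. The reasons for lateness lie with the patient. Without a patient term, on-time versus late rows partly compare different kinds of patients as well as different timing.

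Aim 6 is meant to guide assessment windows in future pragmatic trials. A spurious timing effect, or a spurious finding that the treatment effect depends on punctuality, would mislead that use directly.

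**Working it through.** **The plan's own figures.** The plan gives no error rate, correlation or alpha for Aim 6, so there is nothing of that kind to reproduce. Its sample size (section 11.2) is 152 required, 28% drop-out and 210 enrolled. Here 152/(1 - 0.28) = 211.1, and 210 x 0.72 = 151.2, so the three figures agree closely.

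**Inputs.**
- From the plan: m = 5 assessments per patient (4 if baseline becomes a covariate).
- Assumed: within-patient correlation of the outcome, r_y = 0.3 to 0.7.
- Assumed: within-patient correlation of the on-time indicator, r_x = 0 to 0.7.
- Assumed: two-sided alpha 0.05, and 60% of assessments inside the narrow window.

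**Formula.** For pooled least squares with exchangeable correlation, the true variance of the timing coefficient exceeds the reported one by

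DE = 1 + (m - 1) x r_y x r_x,

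and the actual error rate is 2[1 - Phi(1.96/sqrt(DE))].

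**Worked cases, m = 5.**
- r_x = 0: DE = 1, error 5.0% for any r_y.
- r_y = 0.5, r_x = 0.7: DE = 1 + 4 x 0.35 = 2.40; 1.96/1.549 = 1.265; error 20.6%.
- r_y = 0.7, r_x = 0.7: DE = 1 + 4 x 0.49 = 2.96; 1.96/1.720 = 1.139; error 25.5%.

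**Formula against simulation.** The simulation used 152 patients, five complete visits, no true effects and 1,500 runs per cell. Its Monte Carlo standard error is about 0.6 points at 5% (sqrt(0.05 x 0.95/1500)) and 1.0 point at 20% (sqrt(0.2 x 0.8/1500)). Cells show formula; simulated timing / interaction, in percent.

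| r_y | r_x = 0 | r_x = 0.3 | r_x = 0.5 | r_x = 0.7 |
|---|---|---|---|---|
| 0.3 | 5.0; 5.6 / 6.0 | 9.3; 9.9 / 8.9 | 12.1; 12.1 / 11.0 | 14.8; 12.7 / 15.8 |
| 0.5 | 5.0; 4.8 / 5.3 | 12.1; 13.5 / 10.6 | 16.6; 16.3 / 15.5 | 20.6; 20.5 / 20.5 |
| 0.7 | 5.0; 5.1 / 5.5 | 14.8; 14.0 / 15.3 | 20.6; 21.8 / 20.4 | 25.5; 25.3 / 25.3 |

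With m = 4 the r_x = 0.7 column of the formula becomes 12.5%, 17.1% and 21.2%.

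**Closer to the plan's numbers, and testing the remedy.** With 210 patients, up to five visits, 28% drop-out, r_y = 0.3 to 0.7 and r_x = 0, 0.4 or 0.7, pooled regression rejected in 5-24% of runs for timing and 4-25% for the interaction. Patient-clustered errors gave 4-6%, and a patient random effect gave 4-6%. When the 0.7 lateness correlation was placed on an underlying latent scale, which implies a weaker correlation in the on/off indicator, pooled regression gave 11-20% and clustered errors roughly 3-7%.

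**Alpha.** In Aims 1 and 2, "alpha will be set to 0.025 for each test of the outcome variables"; Aim 6 is silent. At 0.025, with m = 5 and r_y = 0.5, the formula gives 2.5%, 7.6%, 11.3% and 14.8% across r_x = 0, 0.3, 0.5 and 0.7. The relative inflation is larger (14.8/2.5 = 5.9 times).

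**The case against.** The best reply is that the plan never says the visits are pooled. Coding a flag for each observation describes how a variable is built, not how rows enter the model. The timing table sets its windows visit by visit, which would suit one regression per visit. The interaction sentence also speaks of participants who keep to the narrow schedule, which is patient-level language, and Aim 2 uses the same model for baseline predictors. One regression per visit has one row per patient and none of this problem.

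That stands as a limit on the claim. A reader might infer that the plan commits to an ordinary pooled regression with wrong standard errors; the text does not go that far. But it does not say one model per visit either, a per-observation indicator most naturally implies stacking, and a patient-level reading would need a rule for patients who are on time at some visits and late at others.

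It can also be said that lateness may be a one-off event: a conflict that delays the start of treatment need not delay later assessments, whose windows are tied to the FR dates. That is fair. With no clustering of lateness, both tests stay near 5%. The reasons the plan gives make some clustering plausible, but they do not measure it.

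Finally, Aim 6 states no hypothesis or alpha and speaks of relative importance. This limits the consequence. It does not remove the issue, because asking whether the intervention effect differs by timing is an inferential question whose answer depends on its standard error.

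**Conclusion.** The point holds conditionally. Aim 6 names a model with no provision for repeated observations per patient, although the plan recognises that need in Aim 1. If visits are pooled, the false-positive rate for timing and timing-by-intervention lies between the nominal 5% and about 20-25%. This assumes exchangeable correlation, r_y of 0.3 to 0.7, r_x of 0 to 0.7 and two-sided alpha 0.05. Separately, the timing contrast then mixes timing with patient type.

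Two stronger readings are not supported. A reader might take a fourfold inflation as a ceiling or as a property of the plan. It is neither: it needs r_y x r_x of about 0.335 at m = 5, the documents give neither correlation, and the true figure could be lower or higher. A reader might also infer that the estimated treatment effect is compromised. A pooled model would indeed test arm badly (16-32% false positives in simulation), but Aim 6 does not pose that test. The arm effect belongs to Aim 1, where the 3-month primary analysis uses the HLM and is untouched. The point should be corrected before Aim 6 is analysed; it does not threaten the trial's main conclusion.

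**What to change.** In the Aim 6 Analytical Technique, replace the sequential multiple regression with the Aim 1 HLM for continuous outcomes: patient random effect, visit as a factor, arm, arm-by-visit, the timing indicator, and timing-by-arm. The arm-by-visit term is needed so that the arm effect is not averaged over baseline, where randomization implies none. Patient-clustered standard errors are an acceptable alternative for the error rate, but they do not address the mixing of timing with patient type. For non-continuous outcomes such as medical board status, use the matching generalized mixed model or GEE.

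Splitting timing into each patient's on-time share and the visit-level deviation from it can be a sensitivity analysis; it shows how much of any timing effect is between patients. State the alpha, and whether baseline is an outcome row or a covariate. If one regression per visit was intended, say that instead.

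The cost is wording only. The HLM is already in the plan, and no new data are needed.

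### Aim 6 names no baseline score in its follow-up timing comparison, so pre-existing patient differences may be read as a timing effect and precision is lost

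*Combined protocol and SAP*

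**What the plan says.** Section 11.3 specifies a sequential multiple regression for Aim 6: "We will assess the relative importance of the timing of assessments on our primary outcomes of pain and physical function", and likewise on a list of secondary outcomes. Two model terms are named. The first is the timing variable: "We will code an indicator variable to document every observation that occurs within the narrow timeline". The second is its product with treatment: "We will use an interaction term of this indicator with the intervention". No baseline score and no other patient covariate appears.

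Two other aims in section 11.3 use the same technique and do name their controls. For Aim 2, "The model will adjust for baseline measures of the co-primary outcomes and pre-FR treatment groups". For Aim 5, the delivery schedule is assessed "controlling for treatment group on our primary outcomes of pain and physical function". Nothing says that the Aim 2 covariates carry over to Aim 6.

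The Aim 6 text also explains why collection went off schedule. Baseline measures were early relative to treatment because of "conflicts such as military training exercises, personal or family illness or planned leisure travel which postponed the start of study treatment". For the later visits, "Collection of follow-up measures was sometimes earlier or later than desired", because patients with conflicts were not available when the measures were requested. The timing table has five windows: baseline, end of pre-FR, end of FR, and 3 and 6 months after FR. Section 10.1 schedules the patient-reported outcomes for all patients before randomisation, so the baseline scores exist.

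**The concern.** Being inside or outside the narrow window is an observed patient characteristic, not an assigned condition. Patients who could not attend on schedule may have differed in pain or function before any treatment. The plan itself expects baseline status to matter for outcome: Aim 2 in section 9.4 anticipates poorer response in those with worse distress and disability at the start, and section 9.3 cites studies linking higher pain intensity to worse results a year later. If baseline is related both to window status and to the follow-up score, a model without it assigns part of that difference to timing.

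Aim 6 is meant to guide the choice of assessment windows in future pragmatic trials. A contaminated coefficient could make a harmless window look harmful, or the reverse, depending on which group started worse. Separately, the interaction asks whether the integrative-modality effect depends on timing. It has little power at this sample size, and leaving out a strong predictor that is already collected weakens it further.

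**Working it through.** **What the documents supply.** Section 11.2 requires 152 patients and allows for 28% loss: 152 / 0.72 = 211.1, or 212 for equal arms, against 210 stated. That agrees within two patients, so 152 is used below. The documents give no effect size, SD, baseline correlation, share of scores inside the window or significance level for Aim 6. There is therefore no Aim 6 figure to reproduce.

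**Assumptions (not in the documents).** One follow-up score per patient, outcome SD 1, a 76/76 split inside and outside the narrow window, no true timing effect, a baseline gap of 0.3 SD between the two groups, and a baseline-to-follow-up correlation rho of 0.3, 0.5 or 0.7.

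**Step 1: bias without baseline.** Bias = rho x gap.
- 0.3 x 0.3 = 0.09 SD
- 0.5 x 0.3 = 0.15 SD
- 0.7 x 0.3 = 0.21 SD
- Any rho x 0 = 0

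For gaps of 0.2 to 0.5 SD the range is 0.3 x 0.2 = 0.06 to 0.7 x 0.5 = 0.35 SD.

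**Step 2: false-positive rate of the timing test.** SE = sqrt(1/76 + 1/76) = 0.162. The rejection probability is 1 - Phi(z - bias/SE) + Phi(-z - bias/SE). The two-sided 0.025 level is borrowed from Aims 1 and 2, whose sidedness is also not stated.

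| rho | Bias, 0.3 SD gap | Rejection at 0.025 | Rejection at 0.05 |
|---|---|---|---|
| 0.3 | 0.09 | 4.8% | 8.6% |
| 0.5 | 0.15 | 9.5% | 15.2% |
| 0.7 | 0.21 | 17.2% | 25.3% |

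Across gaps of 0.2 to 0.5 SD, rejection at 0.025 runs from 3.5% to 47%. With a 30/70 split it runs from 3.3% to 40%.

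**Step 3: with baseline in the model.** The residual variance becomes (1 - rho^2) of its unadjusted value, a cut of 9%, 25% or 49%. The formula gives SE = 0.162 x sqrt(1 - rho^2) = 0.155, 0.140 and 0.116. A simulation of 3,000 trials per rho with the 0.3 SD gap gave slightly larger SEs (0.157, 0.143, 0.118), because baseline and window status are then correlated. Bias was about zero and rejection at 0.025 was 2.6%, 2.1% and 2.6%. The zero bias is built in, because in this simulation confounding runs only through baseline.

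**Step 4: the interaction.** With four cells of 38, SE = sqrt((1 - rho^2) x 4/38). Without baseline this is sqrt(4/38) = 0.324. For an assumed interaction of 0.5 SD at two-sided 0.05, power = Phi(0.5/SE - 1.96):
- no baseline: 34%
- rho 0.3: 37%
- rho 0.5: 43%
- rho 0.7: 58%

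A baseline gap that is equal in both arms cancels from the interaction, so this step concerns precision only.

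**The case against.** The best reply is that the Aim 6 text is silent rather than restrictive. It does not list the intervention main effect or the scheduled visit either, so it cannot be a complete list of terms, and a sequential regression naturally takes a first block of covariates. This stands in part: a reader might infer that baseline has been excluded, and the documents do not say so. But section 11.1 is where control of confounding was to be described, and it refers the reader to section 11.3, where Aim 6 names none while Aims 2 and 5 name theirs. An analyst following the text would have no instruction to adjust.

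Other tempting readings also go too far:
- A reader might take illness, training and travel as the stated reasons for off-window follow-up scores. That list is attached to the baseline window; for follow-up the text gives only unspecified conflicts and unavailability.
- A reader might picture a comparison of punctual with late patients who started worse. Off-window follow-up scores could be early or late, and no baseline difference is documented in either direction.
- A reader might treat the rejection rates as those of the planned analysis. They assume one score per patient, whereas the plan codes every observation over repeated visits.

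Two further points stand. The power gain is modest unless rho is high: 43% at rho 0.5 is still low. And Aim 6 is a secondary methods aim, so the treatment comparison in Aim 1 does not depend on it.

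**Conclusion.** The point holds as a gap in the Aim 6 model for the four follow-up windows. Window status was not assigned, the baseline score is collected, and the named terms leave the timing coefficient open to whatever difference already existed between the two groups. The size is conditional: 0.09 to 0.21 SD for a 0.3 SD gap and rho 0.3 to 0.7, larger for a larger gap, and nothing if the groups started alike. The precision loss does not need a gap; it needs only a baseline correlation, and it amounts to a share rho squared of the residual variance.

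It does not extend to the baseline window, where the baseline score is itself the outcome and cannot be its own covariate. Nor would adjustment make the timing coefficient causal: events after baseline stay uncontrolled, and a baseline score taken outside its own window is an imperfect covariate.

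**What to change.** In the Aim 6 Analytical Technique, add text to this effect:

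- For the four follow-up windows, and for each outcome with a baseline value of the same measure, the first block contains that baseline value, randomised arm and scheduled visit. The timing indicator and its interaction with arm enter after it. Aim 2 already does this for baseline and arm.
- The baseline window is analysed separately without this covariate, so that all five windows are still examined.
- The timing coefficient is reported as an association.

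Limiting the covariate to outcomes with a baseline value of the same measure matters because the Aim 6 list includes items such as medical board status and duration of disability, for which such a covariate is not straightforward.

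The cost is a few sentences and a few model terms, with no new data collection. Patients without a baseline score need imputation or drop out of this secondary analysis.
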